Rationale --BP lowering is currently being tested to prevent HE after hypertensive ICH, and drugs are now available (4 Factor Prothrombin Complex Concentrate-4F-PCC and Praxbind) to rapidly reverse the coagulopathy caused by warfarin (4F-PCC) or by other newer oral anticoagulants like Dabigatran (Praxbind). Current standard management is to lower the SBP in our ED to 130-150 mm Hg or to give 4F-PCC (for elevated INR) or Praxbind (when the concurrent use of Dabigatran is suspected) once ICH is confirmed on CT scan. In both the aggressive and standard treatment arms of ATACH, patients will probably receive lowering of SBP to about 150 mm Hg (and lower in the aggressive treatment arm) after arrival to the ED. However, therapy begun in the ED will not result in BP lowering (or coagulopathy reversal) within the first hour of onset, and rarely within the first 2 hours. MSU management will permit such early BP lowering (or coagulopathy reversal) and allow us to assess its results on preventing EHE.

Aim 3: Determine if coagulation status, as measured by thromboelastography (TEG), is more altered very early after the onset of spontaneous (non-coagulopathic) ICH compared to later, and if TEG predicts EHE.

- 3a. We hypothesize that the pro-coagulation response to ICH will be greater soon after the onset of bleeding.
- 3b. We hypothesize that patients without early pro-coagulation changes on TEG will be more likely to develop EHE.

We will compare TEG values in MSU patients studied within the first 2 hours after symptom onset to those studied later, and in patients with EHE to those without. Patients with bleeding due to known coagulopathy or antithrombotic therapy will be excluded from this Aim.

Rationale -- We have shown that ICH is associated with faster and stronger clot formation as measured by TEG, but that patients with HE do not demonstrate this presumably adaptive response to bleeding. It is possible that failure to mount this hypercoaguable state after ICH may be important in leading to HE. This dynamic has never been studied in the first hours after ICH onset when EHE may be more frequent and dramatic than later HE. MSU management will allow us to obtain TEG measurements in the first hours after ICH onset and correlate them with EHE.

Inclusion Criteria:

- 1. Enrollment into MSU study (meeting all inclusion criteria)
- 2. Parenchymal ICH on first CT scan < 60cc
- 3. At least one SBP reading >150 or INR > 1.4 (only for SA 2)

Exclusion Criteria:

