1. Incidence of EHE/HE and change in hematoma volume from baseline to 24 (+ 12 hr) hours in patients having BP treatment (or coagulopathy reversal) started within 2 hours and 2-4 hours of symptom onset (Group 1 or 2) compared to what is expected for each respective time group. We will analyze the entire group of patients treated within 2 hours as a whole, and also those treated within 1 hour and between 1-2 hours separately. We will also calculate the proportion of patients in each group with treatment begun on the MSU. The difference in number of patients with EHE, and in average volume, will represent the number of patients with EHE and the average volume of EHE prevented by earlier (mainly MSU) management.

Aim 3:

1. We will obtain TEG values (R, K, MA, Angle, Delta) in all Group 1 patients with spontaneous ICH (normal INR and no use of DTIs or Factor Xa inhibitors) comparing parameters in those with blood drawn within the first 2 hours versus 2-4 hours after symptom onset, and in patients with EHE to those without in the 0-2 hour group. We will analyze the entire group of patients analyzed within 2 hours of symptom onset as a whole, and also those analyzed within 1 hour and between 1-2 hours separately.

Other variables to be measured in both Group 1 and Group 2 patients:

- 1. Symptom onset time
- 2. Time of enrollment into either MSU or SM arm pre-hospital
- 3. Time of all CT scans

- 4. Hematoma volume, morphology and location on all scans
- 5. Etiology of ICH
- 6. Group 1: BP levels and treatment in MSU and ED for first 2 hours . Group 2: BP levels and treatment by EMS and ED up to the time of first CT scan
- 7. Time from symptom onset to first BP treatment and to first SBP < 150
- 8. Dose and time of any 4F-PCC or Praxbind administration
- 9. NIHSS at time of all CT scans (baseline in both groups, 1 hr CT in Group 1), and at 24 hrs in all pts.
- 10. Use of antiplatelet drugs
- 11. Significant comorbidities, chronic HTN, coagulopathy
- 12. TEG, other baseline coagulation measurements (platelets, INR, PTT)

Sample Size Estimation and Methods (All analyses adjusted for baseline NIHSS, use of antiplatelets, comorbidities; Use logarithmic transformation of hematoma volume to normalize the distribution):

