Aim 1a. If we assume a 30% incidence of HE in the 2-4 hour group, and expect an increase to 60% in the 0-2 hour group, a total of 94 patients (47 per group) adjusting for multivariable analyses will be needed to achieve 80% power to detect this difference with a 0.05 two sided significance value.

Aim 1b. Based on previous studies, the mean \pm SD of the logarithmic hematoma volume in the 2-4 hour group should be 2.9 \pm 1.2. If we expect 30% smaller baseline hematoma volumes in the 0-2 hour group log vol = 2.0), to achieve 80% power, a total of 64 patients (32 per group) adjusting for multivariable analyses will be needed to achieve 80% power to detect this difference with a 0.05 two sided significance value.

Aim 2a. The expected incidence of EHE/HE and volume of hematoma growth will be derived from patients who present within 4 hours of onset (separated into 0-2 hour and 2-4 hour groups) who do not receive acute BP treatment or coagulopathy reversal. If we assume a 60% incidence of EHE in the 0-2 hour group and expect early BP treatment (or coagulopathy reversal) to reduce this to 30%, a total of 94 patients (47 per group) adjusting for multivariable analyses will be needed to achieve 80% power to detect this difference with a 0.05 two sided significance value.

Aim 3. We have previously studied TEG values in ICH patients presenting within 6 hours of onset and compared TEG values for those who developed HE to those who did not. K, which represents speed of clot formation, was significantly slower in patients with HE, with a mean difference of 1.5 ± 3.1 min. Assuming mean K in the 2-4 hour group will be 1.5 min longer than the 0-2 group and that there will be a 1.5 min difference between HE and non -HE patients, then we would expect a 3 min difference between the 0-2 hour EHE patients and the 2-4 hour non-HE patients. A total of 40 patients (20 in each group) adjusting for multivariable analyses will be needed to achieve 80% power to detect this difference with a 0.05 two sided significance value.

Procedures:

- Get baseline MSU CT loaded onto PACS for measurement.
- 2. Obtain careful documentation of BP and BP treatment X first 2 hours Group 1 and up to time of first CT scan in Group 2.
- 3. Obtain accurate history of previous meds, comorbidities, coags, baseline NIHSS.
- 4. Obtain TEG in all Group 1 pts.
- 5. Obtain 1 hr f/u CT and NIHSS in all Group 1 patients.
- 6. Obtain 24hr CT and NIHSS in all pts.

References:

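### ICH substudy (Appendix 4): the effect sizes behind the 80% power claims for Aims 1b and 3 contradict the appendix's own assumptions

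*Protocol*

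**What the plan says.** All of this is in Protocol Appendix 4, mainly under Sample Size Estimation and Methods.

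**Aim 1b** compares baseline hematoma volume between patients scanned at 0-2 hours and at 2-4 hours, on a log scale whose base is not stated. The 2-4 hour mean is 2.9 with SD 1.2. The planned effect reads: "If we expect 30% smaller baseline hematoma volumes in the 0-2 hour group log vol = 2.0". The stated need is 64 patients (32 per group) for 80% power at two-sided 0.05, after an adjustment for multivariable analysis.

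**Aim 3** compares TEG parameters. On earlier data, "K, which represents speed of clot formation, was significantly slower in patients with HE", with a mean difference of 1.5 ± 3.1 min. The time effect is "Assuming mean K in the 2-4 hour group will be 1.5 min longer than the 0-2 group". The appendix adds a 1.5-minute HE effect and concludes: "then we would expect a 3 min difference between the 0-2 hour EHE patients and the 2-4 hour non-HE patients". The stated need is 40 patients (20 per group), again for 80% power.

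The hypotheses set the directions. Hypothesis 3a: "We hypothesize that the pro-coagulation response to ICH will be greater soon after the onset of bleeding". Hypothesis 3b: "We hypothesize that patients without early pro-coagulation changes on TEG will be more likely to develop EHE". The Aim 3 entry under Primary Outcomes lists two comparisons: blood drawn at 0-2 hours versus 2-4 hours, "and in patients with EHE to those without in the 0-2 hour group".

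**The concern.** In Aim 1b the verbal effect and the number entered are different effects. A value of 2.0 is close to 2.9 × 0.7 = 2.03, which suggests that 30% was taken off the log value instead of the volume.

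In Aim 3 the two 1.5-minute effects are added for a pair of groups in which they oppose each other. The contrast that was sized is also not one of the two comparisons the appendix lists for Aim 3.

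Both aims carry an explicit 80% power statement on outcomes the appendix labels primary. If the power for the stated effects is far lower, a null result on baseline volume or on K could be read as evidence of no effect when the substudy had little chance of showing one.

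**Working it through.** Every calculation is a two-sample t-test, two-sided 0.05, unadjusted for covariates unless stated.

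**Reproducing the stated sizes**

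- Aim 1b: difference 2.9 − 2.0 = 0.9, SD 1.2. This needs 29 per group; 29 × 1.1 = 31.9, matching the stated 32.
- Aim 3: difference 3.0, SD 3.1. This needs 18 per group; 18 × 1.1 = 19.8, matching the stated 20.

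The 10% inflation is inferred from the reference to multivariable adjustment. The sizes follow from the differences entered, so the question is whether those differences are the ones described.

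**Aim 1b: log difference against percentage**

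- Log base: 10^2.9 = 794 cc, which cannot be a mean under the entry criterion "Parenchymal ICH on first CT scan < 60cc". Natural logs give exp(2.9) = 18.2 cc.
- As entered: exp(2.0) = 7.4 cc, and 1 − exp(−0.9) = 0.593, a 59% smaller geometric-mean volume.
- As worded: −ln(0.7) = 0.357, so the 0-2 hour log volume would be 2.9 − 0.357 = 2.54.
- Power for 0.357 with SD 1.2: 22% at 32 per group; 30% at 47 per group (if Aim 1a's size fills both windows). Reaching 80% takes 179 per group.

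**Aim 3: direction of the two effects**

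Let a be the mean K in 0-2 hour patients without EHE. Slower clot formation means longer K. Adding the two effects as the appendix does:

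| Group | Expected K |
|---|---|
| 0-2 h, no EHE | a |
| 0-2 h, EHE | a + 1.5 |
| 2-4 h, no HE | a + 1.5 |
| 2-4 h, HE | a + 3.0 |

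The sized contrast is (a + 1.5) − (a + 1.5) = 0. Three minutes separates the other two corners, 0-2 h without EHE and 2-4 h with HE.

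The time effect could instead be read as a difference between whole-window means, using Aim 1a's HE rates of 60% (0-2 h) and 30% (2-4 h). The time effect within HE status is then 1.5 + 0.6 × 1.5 − 0.3 × 1.5 = 1.95, and the sized contrast is 1.5 − 1.95 = −0.45 min. That is still nowhere near 3.

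**Aim 3: power for the two listed comparisons**

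Each has an assumed effect of 1.5 min. Taking 3.1 as the SD of K and splitting the 0-2 h window at Aim 1a's 60% rate:

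| Size assumed | 0-2 h vs 2-4 h | EHE vs no EHE within 0-2 h |
|---|---|---|
| 20 per window | 32% (20 v 20) | 17% (12 v 8) |
| 20 EHE plus 20 non-HE: windows of 20/0.6 = 33 and 20/0.7 = 29 | 46% (33 v 29) | 26% (20 v 13) |
| Aim 1a's 47 per window | 64% (47 v 47) | 36% (28 v 19) |

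At 20 per window, the difference detectable with 80% power is 2.8 min for early versus late and 4.2 min for 12 versus 8. For 1.5 min, 80% power takes 69 per group.

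**The case against.** The strongest objection is to the replacement figures.

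- **Inflation.** If the 10% inflation pays for covariate adjustment, power should be computed at 29 and 18 per group. It is then 20% for Aim 1b and 29% for the Aim 3 time comparison, and Aim 1b's 80% size rises to about 198 per group.
- **EHE rate.** The 12 versus 8 split borrows Aim 1a's 60%. Aim 3 uses Group 1 only, whose patients receive protocolized blood pressure treatment, and Aim 2a expects early treatment to bring EHE down to 30%. At 30% the split is 6 versus 14, with power 16% and a detectable difference of 4.5 min. With 30% in both windows, the 0.45-minute figure becomes 0.

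Both points are fair and show that the Aim 3 numbers are illustrative. They move power by at most about three points and leave it further below 80%.

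A second objection is that simpler explanations exist. Log 2.0 may be what was meant in Aim 1b, in which case 64 stands and only the percentage is wrong. In Aim 3 the group labels may be transposed, in which case 20 per group does fit a 3-minute contrast. The first is a legitimate repair. The second makes the sentence consistent, but the contrast still matches neither listed comparison. The Aim 3 text beside the hypotheses does give the EHE comparison without the 0-2 hour limit, which would change its group sizes but would not produce the corner contrast.

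Finally, this is one appendix substudy. No stopping rule is tied to 64 or 40, and the SAP does not analyse it. That limits the weight of the point without making the power statements correct.

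**Conclusion.** The concern holds. Aim 1b describes a 30% reduction and sizes a 59% one; for 30%, the stated 32 per group gives about 22% power. Aim 3 sizes a 3-minute contrast that its own assumptions put at about zero, and neither listed comparison reaches 80% power for 1.5 min under any of the group sizes examined (17% to 64%).

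This rests on natural logs (the base is inferred), equal SDs on the log scale with percentages read as geometric means, additive effects in Aim 3, and 3.1 taken as the SD of K. The cancellation in Aim 3 does not depend on the SD. Only K was sized, so nothing follows for the other four TEG parameters. The main trial's sample size is not affected. The correction should be made, because the stated power is not the power for the stated effects.

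**What to change.** Amend the wording of Appendix 4; no patients or procedures are added.

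- **Aim 1b:** choose one statement. Either say the aim is sized for a log difference of 0.9, about a 59% smaller geometric-mean volume, and keep 64. Or keep 30%, write the 0-2 hour log volume as 2.54, and state about 22% power at 32 per group. State the log base either way.
- **Aim 3:** delete the 3-minute contrast. For each comparison listed under Primary Outcomes, give the detectable difference and the power for 1.5 min at its own expected group sizes. Declare that 3.1 is taken as the SD of K and which EHE rate is assumed. As an example at 20 per window: 2.8 min and 32% for 0-2 h versus 2-4 h; 4.2 min and 17% for EHE versus no EHE within 0-2 h at 12 versus 8 (60% EHE).
- State whether the power figures are before or after the allowance for multivariable adjustment.

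The only cost is a less favourable power statement.

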Appendix 5—Interosseous tPA administration substudy

Intraosseous administration of tPA for the BEST-MSU Study (IO-MSU Substudy)

I. Background and Rationale

The current protocol for HSC-MS-13-0322, the Benefits of Stroke Treatment Delivered Using a Mobile Stroke Unit Compared to Standard Management by Emergency Medical Services: The BEST-MSU Study, requires intravenous (IV) administration of alteplase. In an urban prehospital setting, intravenous access by paramedics has an estimated initial attempt rate ranging from 77.4-89% success rate, 1,2 with an average time to insertion of 4.4 ± 2.8 minutes. Intraosseous (IO) administration of medication offers an alternative to IV access in the prehosptial environment. Success rates for initial IO administration ranges from 84%-97% 4 5 with the battery powered devices (EZ-IO) offering increased efficacy in speed of administration.

Thrombolytics have been administered through the IO route safely for pulmonary embolism and myocardial infarction with no complications. ^{7 8} The major concern for adverse effects relates to the potential for thrombolytic extravasation. Another case with both epinephrine and thrombolytic therapy through the IO resulted in significant soft tissue necrosis. ⁹ However the extravasation rates of drug administration from IO is a relatively rare occurrence if the needle is properly placed. ¹⁰ The goal of the emergency mobile stroke unit is efficacious and timely of administration of thrombolytic therapy. ¹¹ This protocol addition to the current study will allow for IO placement and infusion of alteplase in patients who are unable to have an IV successfully placed after two attempts prehospitally.

Analysis

This protocol will utilize the patient level data collected from the BEST-MSU study. Only patients who had an IO placed with successful medication will be included. Analysis will include a report of the number of IV attempts made, the number of IO attempts made, and the record of success of infusion and in hospital complications related to the infusion.

II. Objectives

The primary objective of protocol is to provide IO as a route of alternative administration of alteplase in a patient without IV access.

Aims/Outcomes:

The investigators will assess the following outcomes from this protocol

- Number of IO lines place
- The number of successful infusions of alteplase via IO
- The number of complications related to IO infusion of alteplase.

In addition, this study will help to:

 Guide revisions or continued implementation of IO thrombolytic therapy both prehospital and in hospital.

III. Study Population

Inclusion criteria

All patients enrolled under the current HSC-MS-13-0322 trial who cannot have an IV placed successfully after two attempts.

Exclusion criteria:

- Infection of wound at site of IO placement
- Fracture or suspected fracture at IO site
- · Previously attempted IO at site

IV. Protocol Design

All prior protocols from HSC-MS-13-0322 will remain unchanged. IV access will be attempted twice on a patient qualifying for alteplase administration based on the already established trial protocol. If IV access is unsuccessful, IO access will be attempted using the EZ-IO device at the proximal tibia , just medial and inferior to the anterior tibial tuberosity or the proximal humerous. The paramedic will be permitted a maximum of two attempts with IO. On second attempt the other tibial site must be used for placement. Prior to alteplase infusion, withdrawal and successful saline flush must be demonstrated to ensure proper IO placement. To reduce the pain that may be associated with initial infusion 10cc of 1% Lidocaine without epinephrine will be infused after verification of the IO line. The IO will be left in place until at least two hours after completion of the alteplase infusion. In the event of alteplase extravasation, the infusion will be stopped immediately, the IO will be left in place and saline will be infused through the IO.

V. Procedures

Data collection

The treating provider will report the number of IV and IO attempts if IV was failed to be placed **Data Analysis**

Investigators will conduct data analysis to measure the outcomes and any adverse events associated with IO infusion

Reports and Publication

Investigators will participate in developing reports and research articles for academic and emergency medicine journals. Data will only be reported and/or published on an aggregated level.

VI. Benefits/Risks/Informed Consent Benefits

Data generated from this outcomes research will potentially improve the care of stroke patients in the prehospital environment who require thrombolytic administration but are unable to have an IV established

Risks

The major risk is the potential for extravasation of alteplase through an incorrectly placed IO.

VII. References

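### The intraosseous substudy selects its analysis set on its own outcome: failed placements are excluded and, on the natural reading, so are infusions stopped for extravasation

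*Protocol*

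**What the plan says.** The Analysis paragraph of Protocol Appendix 5 sets the analysis population: "Only patients who had an IO placed with successful medication will be included." It does not define success of medication. The next sentence has the analysis report the numbers of IV and IO attempts, together with "the record of success of infusion and in hospital complications related to the infusion".

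Section II of the appendix lists three outcomes: the number of IO lines placed, "The number of successful infusions of alteplase via IO", and "The number of complications related to IO infusion of alteplase". Section III defines a wider population: "All patients enrolled under the current HSC-MS-13-0322 trial who cannot have an IV placed successfully after two attempts", less three site-related exclusions. Section IV adds that "The paramedic will be permitted a maximum of two attempts with IO", and that "In the event of alteplase extravasation, the infusion will be stopped immediately". Section VI states that "The major risk is the potential for extravasation of alteplase through an incorrectly placed IO".

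Section V (Data Analysis) says that adverse events associated with IO infusion will be analysed, but it names no analysis set. The SAP does not mention this substudy.

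**The concern.** The analysis set is defined by one of the outcomes that it is meant to measure. A proportion of successes computed among patients chosen because they succeeded is 100% whatever the true rate. A complication count taken in the same set can miss the event of most interest, because the appendix has an extravasating infusion stopped, and a stopped infusion is not naturally called successful.

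Appendix 5 says the results should help decide whether IO thrombolysis is revised or continued, both before and in hospital, and it plans aggregate reporting only. A reader of the report could not recover the excluded patients. Where the restriction has an effect, it favours the IO route: success looks higher and complications look fewer.

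**Working it through.** The appendix gives no sample size, power or target rate, so there is no planned figure to reproduce. The check is who leaves the analysis, and how much that could matter.

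**Who is in and who is out**

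| Patient | In the Section III population? | In the analysis set if *successful* means completed? | In the analysis set if it means only that drug was given? |
|---|---|---|---|
| No IO line after two attempts | Yes | No | No |
| Line placed, infusion started, stopped for extravasation | Yes | No | Yes |
| Line placed on the second attempt, infusion completed | Yes | Yes | Yes |
| Infusion completed, later complication | Yes | Yes | Yes |

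The first row is excluded on either reading. The second row depends on the undefined term.

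**Size of the first exclusion**

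Input: the Background section of Appendix 5 cites initial IO success of 84-97%, taken here as s, the first-attempt success probability. Two attempts are allowed (Section IV). Assumption: attempts are independent.

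Probability of no line after two attempts = (1 − s)²

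- s = 0.84: 0.16² = 0.0256, or 2.6% of patients
- s = 0.97: 0.03² = 0.0009, or 0.1% of patients

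A failed first attempt followed by a successful second one stays in the set.

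**Size of the second exclusion (completed-infusion reading)**

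The documents give no extravasation rate, so this part is illustrative. Let e be the share of started infusions stopped for extravasation (assumed 1%, 5%, 10%), and c the rate of other complications among the remaining infusions (assumed 0% or 2%). Every placed line is taken to lead to a started infusion.

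Completion over all attempted patients = [1 − (1 − s)²] × (1 − e)

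Complications over started infusions = e + (1 − e) × c

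In the restricted set, completion is 100% and the complication rate is c.

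| e | Completion, s = 0.84 | Completion, s = 0.97 | Completion, restricted | Complications, c = 0 (restricted: 0%) | Complications, c = 2% (restricted: 2%) |
|---|---|---|---|---|---|
| 1% | 0.9744 × 0.99 = 96.5% | 0.9991 × 0.99 = 98.9% | 100% | 1% | 3.0% |
| 5% | 0.9744 × 0.95 = 92.6% | 0.9991 × 0.95 = 94.9% | 100% | 5% | 6.9% |
| 10% | 0.9744 × 0.90 = 87.7% | 0.9991 × 0.90 = 89.9% | 100% | 10% | 11.8% |

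Under these assumptions the restricted set shows the same complication rate whatever the value of e. That is the defect: the analysis would carry no information on extravasation that stops an infusion.

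**The case against.** The strongest reply is that *successful medication* may mean only that drug was given through the IO line. Two places support this. Reporting a record of infusion success would be pointless if every included infusion had been completed, and Section V speaks of any adverse event associated with IO infusion. On that reading a started infusion stopped for extravasation stays in. This stands as a limit: the loss of extravasations is conditional on the completed-infusion reading. It does not remove the point, because failed placements are still excluded and nothing in either document withdraws or explains the restriction.

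A reader might infer from the 84-97% range that 3-16% of patients would vanish. The documents do not support this. The range concerns initial success, a second attempt is allowed, and the number of attempts is reported.

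A reader might also infer that the complication rate would be zero by design. It would not, because complications after a completed infusion remain in the set.

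A failed placement should carry no alteplase complication either, since Section IV requires withdrawal and a saline flush before infusion. Excluding it affects placement success, not infusion safety.

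Finally, the substudy is descriptive. Its outcomes are worded as counts, and it tests no hypothesis. Adverse events are collected independently under Protocol Section 8.F and the Activase safety reporting section. All of this stands and limits the consequence to the substudy's own report.

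**Conclusion.** The concern holds for the substudy's analysis set. The restriction conflicts with the population and outcomes of the same appendix. Placement success is 100% by construction on any reading. About 0.1-2.6% of patients would be lost for want of a line, given the cited 84-97% and independent attempts.

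On the natural but not the only reading, infusion success is also 100%, and infusions stopped for extravasation leave the analysis, which biases the complication count downward. The documents give no extravasation rate, so the size of that bias cannot be derived; the tabulated rates of 1-10% are assumptions.

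It might be inferred that the trial's safety reporting is compromised. The documents do not support that: trial-level adverse event reporting does not depend on this analysis set, and the primary result is unaffected.

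**What to change.** Replace the restricting sentence in Appendix 5 so that the analysis includes every patient in the substudy population with at least one IO attempt. Then:

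- define a successful infusion, and say how a started but stopped infusion is classified;
- report placement success and infusion completion over all patients with an IO attempt;
- report infusion-related complications, including extravasation, over all started IO alteplase infusions. Using all attempted patients here would dilute the rate with patients who received no alteplase through the line;
- report placement complications over all attempted lines.

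The change is to analysis and reporting only; no clinical procedure changes. The cost is small but not nil. Section V has the provider report only IV and IO attempt counts, so infusion start, completion and the reason for stopping must be recorded alongside them.
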